7.5 Discontinuance of HCQ

Patients may choose to discontinue HCQ for any reason, and HCQ will be discontinued if a known contraindication arises. Study procedures should otherwise continue. This is not the same as withdrawal from the study.

7.6 Withdrawal from study.

Patients may withdraw from the study at any time. Data recorded up to the time of withdrawal will be included in the study analysis.

UTAH One (Understanding Treatment And Health in the Ongoing coroNa Epidemic): A Hydrochloroquine Outpatient Study

7.7 Protocol deviations and violations.

The investigator will not implement any deviation from, or changes of the protocol without prior review and documented approval/favorable opinion from the IRB of an amendment, except where necessary to eliminate immediate hazard(s) to study subjects or research personnel,, or when the change(s) involves only logistical or administrative aspects of the trial (e.g., change of telephone number(s)). Protocol deviations will be reported to the DCC within 24 hours of the site becoming aware of the deviation. The study team will provide explanation of the deviation to the DCC. The DCC will notify the IRB of protocol deviations that have potential impact on human subjects safety or trial integrity. The investigator may implement a deviation from, or a change of, the protocol to eliminate immediate hazard(s) to trial subjects without prior IRB approval/favorable opinion. As soon as possible, the implemented deviation must be reported to the DCC, which will notify the medical monitor and the IRB.

8.0 Adverse Events

Patient safety is central to this study protocol.

8.1 Adverse event reporting. Adverse events will be recorded from randomization through day 14 or hospitalization, whichever occurs first. The following adverse events will be collected in the adverse event case report forms and entered into the DCC electronic data capture system:

- Serious adverse events
- Non-serious adverse events that are considered by the investigator to be related to study drug or study procedures or of uncertain relationship
- Adverse events that lead to permanent discontinuation of the study drug.

The following adverse events will be collected prospectively as part of the study-specific outcomes and do not require additional adverse event reporting with the DCC unless they meet criteria for being serious (defined below):

- Rash
- Symptomatic hypoglycemia
- Seizure
- Cardiac arrhythmias
- Worsening requirement for oxygen supplementation and support
- Nausea/vomiting
- Impaired vision

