8.2 Serious Adverse Events

All serious adverse events (SAE) will be reported to the DCC. As per federal definitions (primarily in 21 CFR 312.32(a)), a **serious** adverse event is any adverse event that results in one of the following outcomes:

- Death
- A life-threatening event, one that places the subject at immediate risk of death (this does not include an event that, had it been more serious, would have placed the subject at immediate risk of death)
- Prolonged inpatient hospitalization or rehospitalization

UTAH One (Understanding Treatment And Health in the Ongoing coroNa Epidemic): A Hydrochloroquine Outpatient Study

- Persistent or significant disability/incapacity, indicating a substantial disruption of a person's ability to conduct normal life functions (i.e., the adverse event resulted in a significant, persistent or permanent change, impairment, damage or disruption in the patient's body function/structure, physical activities and/or quality of life).
- Important medical events that may not result in death, be life-threatening, or require hospitalization may be considered serious adverse events when, based upon appropriate medical judgment, they may jeopardize the patient and may require medical or surgical intervention to prevent one of the outcomes listed in this definition.

SAEs must be reported to the DCC within 24 hours of becoming aware of the SAE. This may be accomplished by telephone call or email and can be succinct notification.

Investigators must assess serious adverse events for expectedness and relatedness. Expected SAE include known side effects of study drug as well as clinical events consistent with worsening of COVID, or consistent with pre-existing co-morbidities of individual patients. Relatedness must be assessed by an investigator, and is based on clinical judgment that the event is related to having participated in this study. This is assessed as not related, possibly related, and related. This information must be provided to the DCC within 48 hours of becoming aware of the SAE.

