Deaths from worsening of viral infection or underlying co-morbidities are expected, and do not automatically require expedited reporting. Sudden deaths or deaths believed related to cardiac arrhythmias must be reported to the DCC within 24 hours of becoming aware of the death. The DCC or medical monitor will report these deaths to the DSMB chair within 24 hours of notification. As these are expected complications of study drug, these do not require expedited reporting to the FDA or IRB as described in the next paragraph.

Serious adverse events that are unexpected and related to study participation must be reported to the FDA and the IRB within 7 days of the DCC becoming aware of the classification of the SAE. The DSMB chair will also be notified. All other SAE do not need to be reported to the IRB or FDA. All SAE will be tabulated by study arm and presented to the DSMB at its regular meetings.

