Appendix 1. Visit schedule

Procedure	Visit					
	Baseline	Daily through 15 days	14 days	Hospitalization	28 days	6 months
Screening procedures	X					
Informed consent	X					
Data collection	X	X	X	X	X	X
Active Adverse Event review		X				
Passive Adverse Event review				X		
EQ-5D-5L, PHQ-9, GAD 7, PLC 5	X				X	X

EQ-5D-5L: EuroQol-5 dimensions-5 level; PHQ-9: Patient Health Questionnaire-9, GAD 7: Generalized Anxiety Disorder 7-item scale, PLC 5: PTSD Checklist for DSMB-5 scale

UTAH One (Understanding Treatment And Health in the Ongoing coroNa Epidemic): A Hydrochloroquine Outpatient Study

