Appendix 2: Biospecimen collection schedule:

Study Events	Day	0	1	2	3	4	5	6	7	8	9	10	11	12	13	14	28	6 months
		HCQ or Placebo																
COVID-19 PCR swab positive		1																
Inclusion / Exclusion criteria		1																
Informee consent discussion / signatures		1	1															
Adverse event review			1	1	1	1	1	1	1	1	1	1	1	1	1	1	1	1
Surveys (EQ-5D-5L / PHQ-9 / GAD7 / PLC5)				1													1	1
HCQ or Placebo administration				1	1	1	1	1										
Research Specimen Collection																		
Oropharyngeal self-swab for SARS-CoV-2			1	1	1	1	1	1	1	1	1	1	1	1	1	1	1	
Household contact over age 18 oropharyngeal self-swab for SARS-CoV-2			1	1	1	1	1	1	1	1	1	1	1	1	1	1	1	
Peripheral blood (PBMC / plasma biobank)	40 mL (five yellow top ACD tubes)		1						1								1	1

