2.1.5 Safety Outcome(s)

In addition to the following list, it should be noted that some of the secondary and exploratory outcomes also pertain to safety but are not necessarily restated here.

- Adverse event(s) by 14 days
- Mortality by 28 days
- Hospital admission by 28 days

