7.5.2 Adverse Events

Per the protocol, AEs will be recorded through the earlier of hospitalization and Day 14.

Collected adverse events The protocol identifies adverse events (AEs) to be collected in AE report forms of the database. These include

- Serious adverse events (SAEs)
- Non-serious AEs judged by investigator as related to study drug or study procedures or of uncertain relationship
- AEs resulting in permanent discontinuation of study drug

Summaries Formal statistical analysis of adverse events is not planned, other than what has been noted previously in this SAP for adverse events that are used to define trial outcomes. However, descriptive summaries of adverse events will be created to assist the DSMB in monitoring safety.

For the closed session of DSMB meetings the overall number and percentage of patients with AEs and SAEs will be summarized, overall and by Medical Dictionary for Regulatory

Activities (MedDRA) coding. AEs will be classified by relatedness, expectedness, seriousness, intensity, action taken, outcome, and modification to study treatment. AEs will be summarized by seriousness, relatedness, and expectedness, and SAEs will be summarized by relatedness and expectedness. This will be done by treatment arm for the SAFETY population (principal focus) and for the ITT population. Generic treatment designations are preferred for interim DSMB meetings unless the DSMB requests otherwise.

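### Protocol 8.1 and SAP 7.5.2 stop AE recording at hospitalization, against the AE reviews scheduled in Appendices 1 and 2, and the SAP specifies no table for the events exempt from AE forms

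*Protocol*

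**What the plan says.** **The window.** Protocol 8.1: "Adverse events will be recorded from randomization through day 14 or hospitalization, whichever occurs first". SAP 7.5.2 takes this over: "AEs will be recorded through the earlier of hospitalization and Day 14".

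**Other text on the same subject.**
- Protocol Appendix 1 has a row "Passive Adverse Event review" marked in the Hospitalization column.
- Protocol Appendix 2 has a row "Adverse event review" marked on days 1 to 14, on day 28 and at 6 months.
- SAP 2.1.5 lists "Adverse event(s) by 14 days" with no mention of a stop at admission.
- Protocol 8.2 says "All serious adverse events (SAE) will be reported to the DCC" and sets no end date. Its seriousness criteria include "Prolonged inpatient hospitalization or rehospitalization". It adds a separate rule: "Sudden deaths or deaths believed related to cardiac arrhythmias must be reported to the DCC within 24 hours".
- Protocol 5.4 leaves it to the treating team whether study drug goes on after admission. Appendix 3B foresees interacting drugs being ordered for inpatients during the 5-day treatment period.

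**The exempt events.** Protocol 8.1 keeps seven kinds of non-serious event off the AE forms, on the ground that they are gathered as study outcomes: rash, symptomatic hypoglycemia, seizure, cardiac arrhythmias, worsening oxygen need, nausea/vomiting and impaired vision. Protocol 5.5 lists the events that the daily assessments solicit. Protocol 6.0 promises AE counts with emphasis on the package-insert risks. SAP 7.5.2 describes summaries of what is entered on the AE forms.

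**The concern.** Hospitalization within 14 days is a secondary outcome of this trial. A rule that ends AE recording at admission makes the length of AE follow-up depend on something that treatment might change. SAP 7.5.2 reports the number and percentage of patients with AEs by arm. If admissions differ between arms, non-serious AEs that start in hospital would be under-counted in the arm with more admissions, possibly while study drug is still being taken.

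The documents also leave open which rule was followed. SAEs are the first category under the 8.1 window, but 8.2 asks for all of them without a limit. A reader of the safety tables could not tell whether in-hospital SAEs are included.

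The exempt events raise a second question. If arrhythmias are off the AE forms and not among the daily questions, non-serious ones may appear in neither source. The other six would be collected, yet no table in the SAP would show them.

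**Working it through.** The plan gives no figure to reproduce here. The check is a comparison of passages, a comparison of two lists, and a rough sizing.

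**1. Windows side by side**

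| Place | AE collection ends | Fits 8.1? |
|---|---|---|
| Protocol 8.1, SAP 7.5.2 | Earlier of day 14 and hospitalization | – |
| Appendix 1 | Passive review at hospitalization | No: conflicts with the hospitalization cut |
| Appendix 2 | 16 reviews, 2 of them (day 28, 6 months) after day 14 | No: conflicts with the day-14 limit |
| Protocol 8.2 | All SAEs, no end date | Unclear which section governs |
| SAP 2.1.5 | 14 days | Short label; omits the cut |

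Appendix 2 has no hospitalization column. It bears on the hospitalization cut only because its marks carry no condition. I do not count the daily-through-15-days column of Appendix 1 as a conflict, because days 0 to 14 are 15 calendar days and this may be labelling.

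The end day itself also needs stating. With randomization as study day zero (Protocol 1.0), day 14 is DayR+14, whereas SAP 5.4 ends 14-day mortality and hospitalization at DayR+13.

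**2. Exempt events against daily questions**

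Protocol 8.1 exempts 7 items. Protocol 5.5 solicits rash, symptomatic hypoglycemia, seizure, oxygen supplementation, nausea, vomiting and impaired vision. Taking nausea and vomiting as one item, that is 6 of the 7. The item left over is cardiac arrhythmias. No protocol or SAP endpoint names them.

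**3. Size, on the literal reading**

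Inputs: 400 participants, 200 per arm (Protocol 2.7); window of days 0 to 14, or 15 days. Total 400 × 15 = 6,000 person-days, 3,000 per arm. An admission on day k loses 14 − k days. The documents give no admission rate and expect few admissions, so the rates and timings below are assumptions.

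- Admissions even over days 1 to 14: mean loss (13 + 12 + … + 0)/14 = 6.5 days.
- Admissions even over days 1 to 7: mean loss (13 + … + 7)/7 = 10 days.

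| Assumed admitted | n of 400 | Lost, days 1–14 | Lost, days 1–7 |
|---|---|---|---|
| 2% | 8 | 8 × 6.5 = 52 (0.9%) | 8 × 10 = 80 (1.3%) |
| 5% | 20 | 130 (2.2%) | 200 (3.3%) |
| 10% | 40 | 260 (4.3%) | 400 (6.7%) |

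Difference between arms, per 3,000 person-days:
- 2% v 5% (4 v 10 admitted): 26 v 65 days, 1.3 points (days 1–14); 40 v 100 days, 2.0 points (days 1–7).
- 5% v 10% (10 v 20 admitted): 65 v 130 days, 2.2 points; 100 v 200 days, 3.3 points.

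These are worst cases for each assumed rate and timing, since they treat every day after admission as unrecorded. I give no count of dosing days that fall outside recording: it depends on which days are dosing days, and the extracted Appendix 2 marks days 2 to 6, which may be a table fault.

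**The case against.** Several stronger readings are tempting, and the documents do not support them.

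- **A reader might infer that 8.2 flatly contradicts 8.1.** It does not. An AE that begins before admission, inside the window, can later result in a prolonged stay or a readmission. What remains is a tension: 8.2 has no end date, and nothing says which section governs SAEs that begin in hospital.
- **A reader might infer that all safety information stops at admission.** Protocol 5.5 drops only the swabs during hospitalization, not the daily assessments. SAP 7.3.2 uses symptom scores observed in hospital where they exist. Active review up to admission and passive review afterwards would be a coherent practice, but no passage says so. AE forms also take only SAEs, non-serious AEs that are related or of uncertain relationship, and AEs leading to permanent discontinuation, so few events are at stake.
- **A reader might infer that non-serious arrhythmias have no collection route.** Protocol 8.1 asserts one, 5.5 does not claim to be exhaustive, and 7.4 says the daily assessments ask about events listed earlier, which may cover the cardiac risks in 7.3. The CRFs could settle this and are not available. Serious arrhythmias remain reportable, and arrhythmia-related deaths have their own rule.
- **A reader might infer that SAP 7.5.2 shuts the exempt events out.** Its list of AE-form categories is not worded as closed. It simply specifies no table for these events.

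It is also fair to say that admissions and deaths are analysed by arm elsewhere in the SAP, and that AE reporting is descriptive. These points limit the consequence. They do not remove the mismatch between 8.1 and the two appendices.

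**Conclusion.** The conflict is real and should be fixed. Protocol 8.1 and SAP 7.5.2 give a window that Appendix 1 contradicts at hospitalization and Appendix 2 contradicts after day 14, and the handling of in-hospital SAEs is not settled. Confidence in this part is high.

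The effect is probably small. On the literal reading, with assumed admission rates of 2% to 10% spread over days 1–14 or days 1–7, about 0.9% to 6.7% of AE person-days are lost, and the arm contrasts tried give gaps of 1.3 to 3.3 points. Continuing daily assessments make the true loss of information smaller. The number of AEs affected cannot be estimated from the documents. The primary and secondary efficacy results are not touched; only the descriptive AE tables are.

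The gap for non-serious arrhythmias is a question for the CRFs, held with moderate confidence. The missing table for the six events that are solicited is plain from the text, and Protocol 6.0 gives a reason to supply it.

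**What to change.** Enrollment has ended (SAP 4.2.4 footnote), and the SAP change log for Version 1.4 says that the primary manuscript had been drafted and results seen. The useful changes are therefore to reporting and to the record.

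1. **Table.** Add to SAP 7.5.2 a by-arm descriptive table of the six daily solicited events, labelled as added after results were viewed. It uses data that the plan already collects and serves the Protocol 6.0 commitment for hypoglycemia and impaired vision.
2. **One window.** Reconcile Protocol 8.1, 8.2, Appendices 1 and 2, and SAP 2.1.5 and 7.5.2 to a single AE window with its end day written relative to DayR. State how in-hospital events and the day-28 and 6-month reviews are handled.
3. **Disclosure.** In the safety report, give the window actually applied, the number per arm truncated at admission, and whether in-hospital SAEs were collected. If the CRFs have no arrhythmia field, say that non-serious arrhythmias were not systematically collected.

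Chart abstraction of in-hospital AEs for admitted participants is optional. Under the assumptions above it would cover about 7 charts (8 × 13/14 = 7.4, since a day-14 admission loses nothing) to 40. It would be post hoc and should be labelled so. Coordinators were not blinded (SAP 3.3), so it should be done without knowledge of arm where possible.

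The cost is one extra table, a few sentences in the report, and wording changes in the sections named.

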5.0 Study Procedures

5.1 Intake medication review.

Prior to randomization, study personnel and/or clinical pharmacists will review medications being prescribed for patients on study to confirm eligibility. Study personnel will advise patients to contact the study team if any new medications are prescribed during the 5 day treatment course so that the medication may be reviewed for risk of prolonging QTc.

5.2 Cardiac review.

Prior to randomization, study personnel will review if patient has electrocardiograms (ECG) and will verify that prolongation of QTc has not been diagnosed clinically or on ECG.

5.3 Randomization.

After obtaining informed consent, participants will be randomized using variable block sizes stratified by patient age group (age ≤ 44, 45-59, 60-74, 75+ years). The randomization system at the Data Coordinating Center will require entry of patient initials, date of birth and sex. This will assure that patients do not attempt to enroll multiple times in order to secure active drug.

5.4 Study drug.

This is an open label, variable block randomized placebo controlled trial. If a participant is admitted to the hospital at any time during the active treatment period, the clinical team will decide whether or not to continue study drug treatment during hospitalization.

Participants randomized to the HCQ arm will receive HCQ 400mg po BID x 1 day, then 200mg po BID x 4 days³. The drug dose (2.4 gm over 5 days) falls at the lower end of doses proposed in various international trials, but it has proven in vitro efficacy, with a ratio of lung tissue trough concentrations to the EC50 (effective concentration to suppress 50% of viral activity) of >20.³

Those randomized to placebo will receive a placebo to be taken on the same schedule.

5.5 Study Assessments.

Coordinators will obtain baseline information at the time of randomization. This will include review of all medications being prescribed for patients on study. Study personnel will advise patients to contact the study team if any new medications are prescribed during the 5 day treatment course so that the medication may be reviewed for risk of prolonging QTc, or having a drug interaction with HCQ (see Appendix 3).

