Our main analysis of adult household contact viral acquisition will be restricted to households with at least 2 adults for which no other adult besides the index study subject tests positive for COVID-19 at baseline. We will evaluate the effect of the hydroxychloroquine intervention on the risk of adult household viral acquisition by applying a Mantel-Cochran-Haenszel test stratifying by the randomization age categories and total number of adults within the household. Results will be presented as relative risks with 95% confidence intervals within each stratum, and then pooled across strata. A secondary analysis will assess the effect of treatment arm on rate of household viral acquisition rates averaged across all adults within the household by using a modified Poisson regression model incorporating correlation between participants in the same household, and controlling for age category and number of household members.

The Statistical Analysis plan will detail additional analyses to be performed, including additional exploratory analysis as well as reporting of six-month outcomes among participants.

Safety—already well established in studies of thousands of patients and in post-marketing surveillance—will be assessed through counts (proportions) of adverse events, with special attention to those listed in the package insert for hydroxychloroquine and careful investigation of any SUSARs. As noted elsewhere in this protocol, safety data will be reported to the trial DSMB after every (approximately) 100 subjects have been enrolled in the trial.

We do not anticipate applying formal stopping rules for either efficacy or futility in this trial. It is expected that the trial will remain open for up to 12 months, as the cyclic nature of the illness is not well understood. Thus, if enrollment is not accomplished in this first wave of infection, the trial will not be suspended for futility, anticipating that subsequent waves may occur and enable full enrollment.

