3.3 Treatment Masking (Blinding)

Because of the expedited timeline for implementing this study, it is infeasible to prepare a placebo in such a way that it is indistinguishable from the HCQ doses. However, study staff are not to inform the subject which treatment arm has been assigned to the subject to make this as nearly single-blinded as possible. For the same reason, it is not practical to implement blinding of research coordinators because they may be involved in preparing the kit (containing, among other study materials, study drug) that is delivered to study participants.

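### Non-serious AEs outside the prospectively collected types are dropped if an investigator, for whom no masking is described, judges them unrelated, so by-arm AE percentages may not be comparable

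*Protocol*

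**What the plan says.** Protocol 8.1 sends three classes of event to the AE form, from randomization to day 14 or hospitalization, whichever is earlier:

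- serious adverse events (SAEs);
- "Non-serious adverse events that are considered by the investigator to be related to study drug or study procedures or of uncertain relationship";
- a third class, which carries no causality condition: "Adverse events that lead to permanent discontinuation of the study drug".

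SAP 7.5.2 repeats the second class: "Non-serious AEs judged by investigator as related to study drug or study procedures or of uncertain relationship".

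Protocol 8.1 then names seven event types that "will be collected prospectively as part of the study-specific outcomes and do not require additional adverse event reporting" unless serious: rash, symptomatic hypoglycemia, seizure, cardiac arrhythmias, worsening oxygen requirement, nausea/vomiting and impaired vision. Protocol 5.5 has all of these except arrhythmia asked about daily.

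On masking, Protocol 5.4 states: "This is an open label, variable block randomized placebo controlled trial". SAP 3.3 says that "it is infeasible to prepare a placebo in such a way that it is indistinguishable from the HCQ doses", that participants are not told their arm, and that blinding coordinators is impractical. Neither document says whether the investigator who judges relatedness is masked.

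On use of the data, Protocol 6.0 says that safety "will be assessed through counts (proportions) of adverse events". SAP 7.5.2 plans numbers and percentages of patients with AEs and SAEs for the DSMB closed session: "This will be done by treatment arm for the SAFETY population (principal focus) and for the ITT population". It plans no formal statistical analysis of AEs beyond those that define trial outcomes.

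**The concern.** An AE percentage can be compared between arms only if an event has the same chance of being recorded in each arm. Here, for part of the non-serious events, recording depends on a causality judgment about the study drug, and nothing in the plan keeps that judgment independent of the arm. An assessor who knows that a participant is on placebo has less reason to suspect the drug. An assessor who is confident of the drug's safety may dismiss events on HCQ. Either way the event is absent from the AE form, and re-analysis of the form cannot restore it.

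Safety is part of the primary objective (SAP 2.1.1), and AEs by 14 days are a listed safety outcome (SAP 2.1.5). The percentages shown to the DSMB and reported at the end could partly reflect attribution habits rather than the drug.

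**Working it through.** **Step 1. Which events pass through the filter.**

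| Event | Recorded on | Depends on relatedness? | By-arm summary in SAP 7.5.2 |
|---|---|---|---|
| Serious | AE form | No | Yes |
| Non-serious, led to permanent discontinuation | AE form | No | Within the AE total; not named as its own summary |
| One of the seven listed types, non-serious | Study-specific outcomes | No | None specified |
| Other non-serious, judged related or uncertain | AE form | Yes | Yes |
| Other non-serious, judged unrelated | Not entered | Yes | Not possible |

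Only the last row is lost. The AE-form total nevertheless mixes filtered and unfiltered events, while the seven unfiltered types have no by-arm table.

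**Step 2. Whether the filter is masked.** Protocol 2.4 and 5.4 say open label. SAP 3.3 describes an approximation to single blinding, which consists of not telling the participant. Protocol 5.7 has coordinators and/or investigators collect the data, and coordinators are unblinded. No blinded causality review appears. Protocol 8.2 gives a three-level relatedness scale for SAEs. Protocol 8.1 does not define an uncertain relationship for non-serious events.

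**Step 3. Possible size.** The plan gives no AE rate, attribution rate or AE power, so there is no figure of its own to reproduce. Inputs:

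- *n* = 200 per arm (Protocol 2.7), used only to turn proportions into counts;
- *p* = true proportion with an event of the filtered kind, the same in both arms: 10% or 20% (assumed);
- *c* = probability that such an event is entered: 0.9 on HCQ, and 0.7 or 0.5 on placebo (assumed).

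Expected recorded count = *n* × *p* × *c*. Apparent risk ratio = true risk ratio × *c*(HCQ) / *c*(placebo). With a true ratio of 1:

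| *c*, HCQ vs placebo | Count at *p* = 10% | Count at *p* = 20% | Apparent risk ratio |
|---|---|---|---|
| 0.9 vs 0.9 | 18 vs 18 | 36 vs 36 | 1.00 |
| 0.9 vs 0.7 | 18 vs 14 | 36 vs 28 | 0.9/0.7 = 1.29 |
| 0.9 vs 0.5 | 18 vs 10 | 36 vs 20 | 0.9/0.5 = 1.80 |

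The ratio does not depend on *p* or *n*. The direction can reverse: 0.7 on HCQ and 0.9 on placebo gives 0.7/0.9 = 0.78. A true ratio of 1.29 would then appear as (0.9/0.7) × (0.7/0.9) = 1.00. These ratios apply to the filtered events. Within the full AE total they are diluted by SAEs and discontinuation AEs, to an extent the documents do not allow one to calculate.

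**Step 4. Whether the data could reveal the problem.** SAP 7.5.2 summarizes AEs by relatedness. A non-serious event judged unrelated enters that summary only if it led to discontinuation. The table therefore cannot show how many events were screened out in each arm.

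**The case against.** The case on the other side is substantial and narrows the point.

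- **Much foreseeable toxicity bypasses the filter.** The seven types overlap with the package-insert risks in Protocol 7.3, and six of them are asked about daily. SAP 5.4 also has seven core symptoms, including diarrhea, tiredness and muscle aches, scored daily in both arms whatever the cause. This stands. It does not remove the concern, because SAP 7.5.2 specifies a by-arm summary for the AE form and none for the seven types.
- **The rule is wider than drug-relatedness.** It admits events related to procedures or of uncertain relationship, and discontinuation AEs enter with no causality condition. A reader might infer that only drug-related events are entered; the text does not support that. An unsure assessor has a category to use, which should raise capture in both arms.
- **The comparison is descriptive.** A reader might infer a raised false-positive rate for a safety test. No formal AE test is planned, so that reading fails. Descriptive percentages by arm can still mislead.
- **The direction is not established.** A reader might infer that placebo events are filtered out and HCQ is made to look worse. Events in either arm can be attributed to COVID-19, and an assessor's beliefs can work either way.
- **Knowledge of the arm is inferred.** No passage says that the investigator knows the assignment. The open-label design makes it likely, but the documents support only that no masking is described.

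**Conclusion.** The concern holds in a limited form. Non-serious AEs that are outside the seven listed types and do not lead to permanent discontinuation are recorded only after an investigator's relatedness judgment that is not described as masked. Following the plan exactly can therefore give by-arm AE percentages that are not comparable. The bias has unknown size and sign. The illustrative risk ratios of 1.29 and 1.80 rest wholly on assumed capture probabilities and an assumed equal true rate; they show what a capture gap would do, not that one exists.

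The relatedness rule does not filter SAEs, discontinuation AEs or the seven listed types. The point does not touch the primary viral-shedding analysis. It is a cheap improvement to how safety is summarized and worded.

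**What to change.** (a) **SAP 7.5.2 and the report.** Base the by-arm safety comparison on categories that do not depend on attribution: all SAEs, AEs leading to permanent discontinuation, and the seven prospectively collected types. Add the missing by-arm table for the seven types, stating its time window and the source of the arrhythmia data, since arrhythmia is not in the daily question list. Present the attribution-filtered non-serious counts separately, and say that they are not comparable between arms because entry depended on a relatedness judgment with no described masking.

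(b) **Any collection still to come (Protocol 8.1).** Record non-serious AEs in both arms regardless of relatedness, and keep relatedness as a descriptive field. The footnote to SAP 4.2.4 says enrollment has ended, so this cannot recover events already left out and matters only if collection continues or the form is reused.

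Part (a) costs one extra table and some wording. Part (b) costs more AE form entries. A relatedness assessor kept unaware of the arm would also address the mechanism, but the documents do not show that one is available without extra staff, so this is not part of the recommendation. Categories free of attribution are not thereby masked: reports and decisions to stop drug could still be influenced by knowledge of the arm, and the report should say so.
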